[name], psychiatrist who has collaborated on several studies of mental health integration in Malawi. The team further includes **[name]**, Scientific Director at UNC Project-Malawi, **[name]**, psychiatrist at the University of Zimbabwe, developer of the Friendship Bench and a leader in developing task-shifting models for treating mental health disorders in low-income countries; **[name]**, Malawian psychiatrist leading mental health reform efforts in Lilongwe; and **[name]**, Assistant Director of Clinical Mental Health Services at the Malawi Ministry of Health. These team members have all collaborated together previously on mental health research and service initiatives in Malawi. Overall this impressive and experienced team is well positioned to successfully implement this high-impact project.

F2. Study Design: We will conduct a clinic-level pilot study among five clinics. Three of the five clinics initially served as primary study sites and were assigned to one of 3 conditions: 1) Adapted Friendship Bench (AFB; n=1 clinic/35 women), 2) Enhanced Friendship Bench (EFB; n=1 clinic/35 women) or 3) Enhanced Usual Care (n=1 clinic/35 women).

In June 2020, it was clear that due to both low patient volume and COVID-19 delays, recruitment targets would not be met at these three sites. Therefore recruitment is on hold at these sites and resources will be focused on launching activities at two new larger sites: Bwaila and Area 18. These sites will employ individual-level randomization of the study intervention. Participants will be enrolled at an ANC visit prior to or including 34 weeks gestation and followed through 6 months postpartum.

F3. Study Setting and Site: The proposed study will be conducted at five public antenatal clinics in Lilongwe District, Malawi: Lumbadzi, Mitundu Nathenje, Area 18, and Bwaila health centers. Each of the five health centers provides ART services to HIV-infected women through the antenatal clinic during pregnancy, and also has separate ART clinics serving non-pregnant HIV-infected adults on the health center grounds. In Malawi, HIV-infected pregnant women typically initiate ART at an antenatal care clinic, and transition to an HIV clinic for care after delivery. Thus, the co-location of antenatal and ART services makes these health centers the ideal locations to serve HIV-infected women as they transition from receiving HIV care prenatally in an antenatal clinic, to postnatally in an ART clinic.

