F11. Sample Size. The primary goal of this R34 proposal is to evaluate the feasibility, acceptability, and fidelity of the adapted and enhanced Friendship Bench intervention to improve PND and engagement in HIV care among HIV-infected women. In Aim 3, we will enroll 92 HIV-infected women with PND in a 2-arm pilot (n=12 total in the clinic-randomized phase, n=40 women per arm in the individually randomized phase) to compare enhanced standard care with the enhanced Friendship Bench intervention. Information on preliminary effectiveness of the intervention across a range of mental health and engagement in HIV care outcomes will be assessed, but interpreted cautiously as effectiveness is not the primary aim of this pilot study. Intervention effectiveness will subsequently be assessed in a large-scale clinic-randomized controlled trial. Given that the objective of this analysis is to estimate feasibility, acceptability, and fidelity of the described interventions, feasible sample sizes (n=40/arm; 92 including both the clinic-randomized and individually randomized phases) were determined according to clinic patient volumes and estimated perinatal depression among women living with HIV in the study setting. Precision estimates for the given sample size are based on two-tailed statistical significance tests and a Type 1 error probability (α) of 0.05. The sample of 92 women (40 per arm) will be sufficient to estimate quantitative measures of feasibility and acceptability with reasonable precision (e.g., confidence intervals around proportions of ± 5 -9 percentage points across all arms, and ± 9 -17 percentage points within a given arm). This margin of error was estimated using a desired sample size of 92 and population feasibility and acceptability proportions ranging from 10 to 50%.

E. Potential Challenges and Solutions

What if women are lost to follow-up (LTFU) between pre and postnatal care? Our proposal directly addresses the high rate of LTFU in the postnatal period^{2,52} for women on Option B+ by providing linkage to care coordination from the antenatal to ART clinic and measuring engagement in care through 6 months postpartum. The information gathered at the pilot stage will help to inform the design of a large-scale randomized controlled trial to improve PND and engagement in HIV care during the peripartum period.

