Research Assistants in Malawi (\$7,200 -100% effort for 12.0 months)- Three research assistants will be hired to conduct mental health screening with the Edinburgh Postnatal Depression Scale and Self-Report Questionnaire-20 and to complete data collection for study visits over a 12 month period. \$200 salary/month x 3 RAs x 12 months = \$7,200.

Total Personnel Costs \$16,800

COMPENSATION FOR STUDY PARTICIPANTS

Study Interview Travel Reimbursement (\$2,100) – A total of 105 participants will be included in our proposed aim. Each participant will receive 7,000 Malawi Kwacha (~\$10/person) as an incentive to participate in the study for each study visit. $\$10 \times 105 \text{ participants} \times 2 \text{ visits (baseline and 6 months)} = \$2,100$.

Counseling Session Travel Reimbursement (\$2,275) - Participants in the EFB arm (n=up to 6 counseling sessions) and the AFB (n=up to 7 counseling sessions) will also receive travel reimbursement as an incentive to attend intervention counseling sessions. $35 \times 5 \times 6 = \$1050 + 35 \times 5 \times 7 = \$1,225$, for a total of \$2,275.

Total Compensation for Study Participants Costs \$4,375

OTHER RESEARCH COSTS

Paper, toner and printing costs (\$1,000) – We have budged \$1000 to cover the costs of paper, toner, and printing costs for all study material, including informed consent forms, screening and enrollment logs, and logs for counselling sessions.

Fuel for study activities (\$500) – We have budged \$500 to cover the costs of fuel for study-related activities, including getting staff to and from study sites and for home visits.

Airtime for study staff (\$525) – We have budged \$500 to cover the costs of airtime for study staff so they can be in contact with one another as needed and with the project coordinator.

Tablets for data collection (\$500) – We have budged \$500 to purchase 3 tablets (\$167 x 3 tablets) to support data collection activities.

Translation and Transcription Fees (\$200) – All study materials including informed consent forms, in-depth interview guides, and the Edinburgh Postnatal Depression Scale will be translated into Chichewa, the local language in Lilongwe, Malawi. Translation fees \$200.

Malawi IRB Fee (\$150) – All research in Malawi must receive ethical approval from the National Health Science Research Committee, which charges a \$150 fee to review all applications for ethical approval.

Total Other Research Costs \$2,875

TOTAL COSTS: \$24,050

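### F11 claims overall precision about 1 point better than 92 women give at 95% confidence; its per-arm upper figure is too wide

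*Combined protocol and SAP*

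**What the plan says.** F11 sets the sample at 92 women: 12 from the clinic-randomized phase and 40 per arm from the individually randomized phase. It says that numbers were fixed by clinic volume and the expected frequency of depression. It then offers a precision statement:

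- The error rate: "Precision estimates for the given sample size are based on two-tailed statistical significance tests and a Type 1 error probability (α) of 0.05".
- The claim of adequacy: "The sample of 92 women (40 per arm) will be sufficient to estimate quantitative measures of feasibility and acceptability", followed by the example "confidence intervals around proportions of ± 5 -9 percentage points across all arms, and ± 9 -17 percentage points within a given arm".
- The basis: "This margin of error was estimated using a desired sample size of 92 and population feasibility and acceptability proportions ranging from 10 to 50" percent.

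No interval method is named, and there is no mention of a finite-population correction, a confidence level other than the one implied by alpha, or an allowance for missing data.

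Figures from the superseded three-arm design remain elsewhere. F2 still describes "Enhanced Friendship Bench (EFB; n=1 clinic/35 women", and the Budget Justification still says "A total of 105 participants will be included in our proposed aim".

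**The concern.** All the inputs to the margin of error stand in one paragraph, so a reader can repeat the calculation. Doing so gives a different answer: the overall half-widths come out wider than stated at both ends, and the per-arm upper end comes out narrower.

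Feasibility and acceptability are primary outcomes (F9.a). Because the sample size was not derived from power, this sentence is the only number in F11 that supports calling 92 women sufficient. The overall figure promises slightly more than the study can deliver at the alpha that the section names. What is at stake is the accuracy of that claim, not the design.

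**Working it through.** **Inputs, all from F11.** Two-sided alpha 0.05, so z = 1.96; n = 92 overall and 40 per arm; p from 0.10 to 0.50.

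**Formula (Wald).** Half-width h = z × √(p(1 − p)/n).

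- n = 92, p = 0.10: 1.96 × √(0.09/92) = 6.13 points. Stated: 5.
- n = 92, p = 0.50: 1.96 × √(0.25/92) = 10.22 points. Stated: 9.
- n = 40, p = 0.10: 1.96 × √(0.09/40) = 9.30 points. Stated: 9.
- n = 40, p = 0.50: 1.96 × √(0.25/40) = 15.49 points. Stated: 17.

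Only the lower per-arm figure is reproduced.

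**Other methods.** As F11 names none, the usual alternatives were computed at 95% (half-widths in points, p = 0.10 / p = 0.50):

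| Method | n = 92 | n = 40 |
|---|---|---|
| Stated in F11 | 5 / 9 | 9 / 17 |
| Wald | 6.13 / 10.22 | 9.30 / 15.49 |
| Wilson | 6.22 / 10.01 | 9.55 / 14.80 |
| Agresti-Coull | 6.41 / 10.01 | 10.12 / 14.80 |
| Jeffreys | 6.13 / 10.08 | 9.29 / 15.04 |
| Continuity-corrected Wald | 6.67 / 10.76 | 10.55 / 16.74 |
| Exact (Clopper-Pearson) | 6.59 / 10.61 | 10.44 / 16.20 |

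The exact value of 6.59 is for 9 of 92 (9.8%); 10 of 92 (10.9%) gives 6.87.

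At n = 92 every method exceeds 6 at the low end and 10 at the high end. At n = 40 only the continuity-corrected interval rounds to 17, and it gives 10.55, not 9, at the other end.

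**Could rounding explain it?** Inverting Wald, n = 1.96² × p(1 − p)/h²:

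- ±5 at p = 0.10 needs 138.3, so 139 women.
- ±9 at p = 0.50 needs 118.6, so 119 women.
- Half-widths that round to 5 and 9 together need n between 115 and 132.
- Half-widths that truncate to 5 and 9 together need n between 97 and 118.

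All of these exceed 92.

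**Internal consistency.** At p = 0.50 the per-arm half-width divided by the overall one should be √(92/40) = 1.52 by Wald, and lies between 1.48 and 1.56 across the six methods. The stated ratio is 17/9 = 1.89. Even taking 17 as 16.5 rounded up and 9 as 9.99 truncated leaves 16.5/9.99 = 1.65. The two upper figures cannot both come from 92 and 40 by any one of these methods.

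**Two possible sources.**

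- A 90% interval gives 5.1 to 8.6 at n = 92, which rounds to the stated range. It contradicts the stated alpha and gives only 7.8 to 13.0 at n = 40.
- The superseded design gives, by Wald, 5.74 to 9.56 for n = 105 and 9.94 to 16.56 for n = 35. Its distances from 5, 9, 9 and 17 are 0.74, 0.56, 0.94 and 0.44, against 1.13, 1.22, 0.30 and 1.51 for 92 and 40. It is closer at three of the four ends, but matching them needs three values truncated and one rounded. The documents do not say that the figures were carried over.

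**The case against.** The arithmetic is not in dispute; the strongest case on the other side concerns weight and scope.

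- **The discrepancy is small and nothing depends on it.** The range is introduced as an example, the sample was set by clinic volume, and ±6-10 would serve a pilot about as well as ±5-9. This stands, and limits the point to a correction of wording. It does not make the figure right: F11 says that the margin was calculated from 92 women and 10% to 50%, so it is a computed result and not a loose illustration.
- **Calling ±17 cautious assumes a full 40 per arm.** F9.a takes acceptability from exit interviews with only some of the women, and gives no number; F4 says all 92 contribute. Wald reaches ±16.8 at n = 34 and ±17.1 at n = 33, so a modest shortfall would make ±17 about right. This stands as a qualification. It does not rescue F11, which ties its figures to 92 and 40, and any shortfall would make the overall ±5-9 more optimistic still.
- **The carry-over explanation is weak.** With ordinary rounding, 105 and 35 give 6-10 and 10-17, which match one stated end of four, no better than 92 and 40. It is inference only, and the conclusion does not need it.

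**Conclusion.** The concern holds. At 95% confidence with 92 women, the overall half-width is about ±6-10 points (Wald) or ±7-11 (exact), not ±5-9. The stated range is too favourable by 1.13 points at p = 0.10 and 1.22 at p = 0.50 by Wald, and by about 1.0 to 1.8 points across the six methods (1.9 if the exact interval is taken at 10 of 92). In relative terms, the stated ±5 understates the Wald value by 1.13/6.13, or about 18%.

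Within an arm of 40, the lower figure agrees with Wald, and the upper figure is too wide by 1.5 points (Wald) or 0.8 points (exact). That error is cautious provided that all 40 women contribute.

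The conclusion rests on F11's own inputs, on reading two-tailed alpha 0.05 as 95% confidence, and on complete data. It is a minor error with no effect on the design or analyses. It should still be corrected, because it concerns the section's only quantitative precision claim.

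**What to change.** Restate the sentence in F11 with one named interval method, at 95% confidence and for proportions of 10% to 50%:

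- Wald: about ±6-10 points for 92 women and ±9-15 points within an arm of 40; or
- exact: about ±7-11 points and ±10-16 points.

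Say that these figures assume complete data. For acceptability, reconcile the denominator in F4 (all 92) with that in F9.a (an interviewed subset), so that the quoted n is the one that will apply. Check whether the present figures were carried over from the design with 105 women, 35 per clinic.

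The cost is a change of wording. The sample size and analyses stay as they are; the stated overall precision becomes about 1 point less favourable under Wald and up to about 2 points under the rounded exact range.
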